#### 4.6 Termination criteria

- 1) The Sponsor and/or the investigator deem it inappropriate to proceed with the trial on medical or ethical grounds.
- 2) The Sponsor and/or the investigator deem it inappropriate to proceed with the study on the basis of scientific reasons or on the basis of factual, accurate or normative considerations for the conduct of the study. For example, major errors in the study protocol (including evaluation criteria, operation, analysis methods, etc.) are found in the trial, so it is difficult to evaluate the drug response; Or a well-designed program, with significant deviations during implementation (including incomplete or unassessable important data), continues, making it difficult to evaluate drug response.
- 3) Due to various reasons (such as funding reasons, management reasons or changes in medical development policies, etc.), the Sponsor decides to terminate the study under the premise of fully protecting the safety and rights of volunteers;
- 4) In accordance with the GCP guidelines and local laws and regulations, the National Medical Products Administration, the Ethics Committee, the investigator or the Sponsor, for any reason, should discontinue the study or discontinue the study in which the volunteers participated, taking into account their rights, the safety and health of the volunteers.

#### 5. Study drugs

#### 5.1 Name of study drugs

#### **Test drug:**

Drug name	Recombinant Human TNK Tissue-type Plasminogen Activator for Injection (rhTNK-TPA)
Trade name	MingFuLe
Strengths	1.0 x 10  IU/16 mg/vial
Storage	Store below 25°C away from light. This product should be used immediately
conditions	after dissolution. If not used immediately, it should be stored in cold storage at 2
	- 8°Caway from light and used within 24 hours.
Shelf life	24 months
Manufacturer	Guangzhou Recomgen Biotech Co., Ltd.
Supplier	Guangzhou Recomgen Biotech Co., Ltd.

#### Control drug:

Drug name
-----------

Trade name	Actilyse ®
Strengths	50mg/vial, 20mg/vial
Storage	Keep in the original packaging. Store below 25°C away from light. It is
conditions	recommended to use the prepared solution immediately after preparation. It has
	been proved that the prepared solution can remain stable at 2-8°C for 24h.
	Frezzing prohibited.
Shelf life	36 months
Manufacturer	Boehringer Ingelheim Pharma GmbH&Co.KG
Supplier	Guangzhou Recomgen Biotech Co., Ltd.

#### 5.2 Labeling of study drugs

The test drug "Recombinant Human TNK Tissue-type Plasminogen Activator for Injection" will be produced and packaged by Guangzhou Recomgen Biotech Co., Ltd. (Sponsor), and the control drug "Alteplase for Injection" will be purchased and provided by Sponsor, and distributed to each clinical research center by the Sponsor.

The outer packing box of the test drug shall be labeled as follows:

For use in TRACE II (0-4.5H) clinical trial only

Please refer to the package insert for using

**Protocol No.: MK02-2020-01** 

Sponsor: Guangzhou Recomgen Biotech Co., Ltd.

The inner packing box of the test drug should be labeled as follows:

**Subject random number:** Product name:

Recombinant Human TNK Tissue-type

Plasminogen Activator for Injection

Strength: Batch number:

1.0 x 10^7IU / 16 mg/vial

**Production date:** Expiry date:

**Storage condition:** store below 25°C away from light

Note: For use in TRACE II (0-4.5H) clinical trial only, protocol number:

MK02-2020-01

#### Guangzhou Recomgen Biotech Co., Ltd.

Note: Please complete the subject random number, batch number, production date and expiration date of the test drug according to the actual situation.

The packing box of the control drug should be labeled as follows:

**Subject random number:** Product name:

Alteplase for injection

Strengths: Batch number:

 $\square$  20mg/vial/ $\square$  50mg/vial

**Production date:** Expiry date:

Storage condition: store below 25°C away from light

Note: For use in TRACE II (0-4.5H) clinical trial only, protocol number:

MK02-2020-01

#### Guangzhou Recomgen Biotech Co., Ltd.

Note: Please select the strength according to the actual dose (20mg/vial or 50mg/vial), and complete the subject random number, batch number, production date and expiration date of the control drug according to the actual situation.

#### 5.3 Method of administration

#### Treatment group (rhTNK-TPA 0.25mg/kg, 25mg at most):

RhTNK-TPA 0.25mg/kg: Each vial is dissolved in 3ml of sterile water for injection to obtain a solution with a concentration of 5.33mg/ml. The amount required for medication is calculated and measured according to the actual body weight of the

subject, 25mg at most. The solution is administered via single intravenous bolus injection in 5-10 seconds.

#### Control group (rt-PA 0.9mg/kg):

RT-PA 0.9mg/kg: The product is dissolved in sterile water for injection to obtain a solution with a concentration of 1mg/ ml. The amount required for medication is calculated and measured according to the actual body weight of the subject. 10% of the solution is injected by intravenous bolus, and the remaining 90% is injected by intravenous drip within 1h.

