#### Control group (rt-PA 0.9mg/kg):

RT-PA 0.9mg/kg: The product is dissolved in sterile water for injection to obtain a solution with a

	concentration of 1mg/ ml. The amount required for medication is calculated and measured according		
	to the actual body weight of the subject. 10% of the solution is injected by intravenous bolus, and the		
	remaining 90% is injected by intravenous drip within 1h.		
	Primary efficacy endpoint:		
	The proportion of subjects with 90-day MRS score of 0-1		
	Secondary efficacy endpoints:		
Efficacy	6 The proportion of subjects with an mRS score of 0-2 at 90±7 days		
endpoints	7 MRS level distribution at 90±7 days (Shift Analysis /Ordinal Distribution)		
	8 The proportion of subjects whose NIHSS score is 0-1 or is improved compared to the baseline		
	with $\Delta$ NIHSS $\geq$ 4 at 24±2h, 7±1d or before discharge (whichever comes first)		
	9 Health-related quality of life (EQ-5d) at 90±7 day		
	The proportion of subjects with a Bathel score ≥ 95 points at 90±7 days		
	The incidence of symptomatic intracranial hemorrhage within 36 hours (as defined by ECASSIII)		
	The incidence of symptomatic intracranial hemorrhage within 90 days (as defined by ECASSIII)		
Safety	The incidence of PH2 intracranial hemorrhage within 36 hours (according to SITS standards)		
	① The incidence of any intracranial hemorrhage within 90 days		
endpoints	① The incidence of significant hemorrhage events at other sites within 90 days (as defined by GUSTO)		
	3 90-day overall mortality		
	Incidence rates of adverse events/serious adverse events within 90 days		
	In this study, rt-PA active control will be used based on a statistical hypothesis test of		
	non-inferiority, and the proportion of subjects with 90-day MRS score of 0-1 will be used as the		
	primary efficacy endpoint.		
Sample size	According to a paper published in the Lancet[7] in 2014 about meta-analysis of the incidence of		
	90-day MRS score of 0-1 (treatment within 4.5h) regarding rt-PA versus Placebo, the RR and 95%		
	confidence interval were 1.24 and 1.14-1.36, respectively. According to the Guidelines for the Design		
	of Non-inferiority Drug Clinical Trials [32], the lower 95% confidence interval of the Meta analysis		
	should be used to calculate the non-inferiority threshold given that the primary endpoint is a high		
	1		

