#### 1.3 Overview of clinical studies at home and abroad

#### (1) NOR - TEST trial [23]

The purpose of the NOR-test was to compare the safety and efficacy of intravenous thrombolysis with tenecteplase and alteplase. NOR - TEST Trial for phase III, multicenter (13) research center, prospective, randomized, open label, end blinded clinical trial, the target population in super acute phase of ischemic stroke (< 4.5 h) patients or symptoms occur within 4.5 h after waking, suspected of acute ischemic stroke and suitable for thrombolysis or thrombectomy bridge before the treatment, according to the proportion of 1:1 randomly given intravenous injection of tenecteplase at 0.4 mg/kg (maximum 40 mg) or alteplase at 0.9 mg/kg (maximum 90 mg). The primary endpoint was the ratio of good prognosis at 90 days (mRS 0 to 1). A total of 1107 patients were enrolled in the study, 7 patients dropped out of the trial, and 1100 patients were randomly assigned to the tenecteplase group (n=549) or alteplase group (n=551). The median age was 77 years (64-79), and the median NIHSS score was 4 (2-8). A final diagnosis of non-ischemic stroke or non-TIA was

found in 99 (18%) patients in the tenecteplase group and 91 (17%) patients in the alteplase group. A total of 354 patients (64%) in the tenecteplase group and 345 patients (63%) in the alteplase group were included in the final outcome analysis.

The results showed as follows: ① The incidence of primary endpoints in the two groups was 64% and 63%(OR 1.08, 95%CI 0.84 to 1.38;P = 0.52);② The 90-day mortality rates were 5% and 5%(P = 0.68), respectively.(3) The incidence of serious adverse events was similar in both groups (26%).

Conclusion: Tenecteplase is not superior to alteplase, and the safety of both is similar. However, in general, the majority of patients in this study were patients with mild stroke, and about 75% of the patients had NIHSS\(\leq\)7 points before treatment, and the proportion of patients with great artery occlusion was small. The research on patients with severe stroke still needs to be continued.

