#### 1.4 Experimental design

In conclusion, this study will evaluate the efficacy and safety of rhTNK-tPA (0.25 mg/kg) compared with standard rT-PA (0.9mg/kg) in the treatment of hyperacute ischemic stroke (within 4.5 h of symptom onset). This is a multicenter, prospective, centrally randomized, open label, blinded-endpoint, active controlled, non-inferior phase III clinical trial.

The drug administration method of the test drug (rhTNK-TPA) is as follows: according to the body weight of the subjects, the final dose is determined at 0.25mg/kg; Each vial is dissolved in 3ml of sterile water for injection to obtain a solution with a concentration of 5.33mg/ml. The amount required for medication is calculated and measured according to the actual body weight of the subject, 25mg at most. The solution is administered via single intravenous bolus injection in 5-10 seconds..

The administration method of active control drug (rt-PA) is as follows: The dose required for medication is calculated and measured according to the actual body weight of the subject based on a standard of 0.9 mg rt-PA/kg. 10% of the dose is injected by intraveno

us bolus, and the remaining 90% is injected by intravenous drip within 1h.

The target population of this study is patients with critical hyperacute ischemic stroke (within 4.5 h of symptom onset), for whom considering the benefit of patients, intravenous thrombolytic therapy should be given as soon as possible after the onset, in order to achieve vascular recanalization or reperfusion and obtain a better prognosis. Due to the different administration methods of test drug and active control drug, and the inconvenience of the double-blind double-dummy design which may delay treatment and is not conducive to the benefit of subjects. Therefore, this study adopts the form of open-label trial. To minimize bias, all endpoints will be evaluated in a blind manner by a qualified study physician.

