### 15. Protocol deviation and violation

All requirements specified in the study protocol must be strictly implemented. Any intentional or unintentional deviation from or violation of the study protocol and the principles of the GCP can be classified as a deviation from or violation of the protocol. In the process of supervision, if the clinical research associate finds any deviation from the program, the investigator or the clinical research associate shall fill in the violation program record, and record in detail the time of discovery, the time and process of occurrence of the event, the reason and the corresponding treatment measures. The investigator shall sign the record and notify the ethics committee. In the data statistics and summary report, investigators analyze and report the impact of the deviation or violation of the protocol on the final data and conclusions.

An assessment should be made when a serious protocol violation occurs. If necessary, the Sponsor may terminate the study in advance.

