#### 5. Design

This study will evaluate the efficacy and safety of rhTNK-tPA (0.25 mg/kg) compared with standard rt-PA (0.9mg/kg) in the treatment of hyperacute ischemic stroke (within 4.5 h of symptom onset). This is a multicenter, prospective, centrally randomized, open label, blinded-endpoint, parallel active controlled, non-inferior phase III clinical trial.

The drug administration method of the test drug (rhTNK-TPA) is as follows: according to the

body weight of the patients, the final dose is determined at 0.25mg/kg; Each vial is dissolved in 3ml of sterile water for injection to obtain a solution with a concentration of 5.33mg/ml. The amount required for medication is calculated and measured according to the actual body weight of the patient, 25mg at most. The solution is administered via single intravenous bolus injection in 5-10 seconds.

The administration method of active control drug (rt-PA) is as follows: The dose required for medication is calculated and measured according to the actual body weight of the patient based on a standard of 0.9 mg rt-PA/kg. The 10% of the dose is injected by intravenous bolus, and the remaining 90% is injected by intravenous drip within 1h.

The target population of this study is patients with critical hyperacute ischemic stroke (within 4.5 h of symptom onset), for whom considering the benefit of patients, intravenous thrombolytic therapy should be given as soon as possible after the onset, in order to achieve vascular recanalization or reperfusion and obtain a better prognosis. Due to the different administration methods of test drug and active control drug, and the inconvenience of the double-blind double-dummy design which may delay treatment and is not conducive to the benefit of patients. Therefore, this study adopts the form of open-label trial. To minimize bias, all endpoints will be evaluated in a blind manner by a qualified study physician.

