#### 9. General considerations for data analyses

All programming will be performed using SAS Version 9.4 or superior. The content of statistical analysis is the general principle of statistical analysis method, and the detail process will refer to protocol. All analysis output will use the following treatment group naming conventions and treatment order:

Treatment group(rhTNK-TPA): RhTNK-TPA 0.25mg/kg: Each vial is dissolved in 3ml of sterile water for injection to obtain a solution with a concentration of 5.33mg/ml. The amount required for medication is calculated and measured according to the actual body weight of the patient, 25mg at most. The solution is administered via single intravenous bolus injection in 5-10 seconds.

Control group(rt-PA): rt-PA 0.9mg/kg: The product is dissolved in sterile water for injection to obtain a solution with a concentration of 1mg/ ml. The amount required for medication is calculated and measured according to the actual body weight of the patient. The 10% of the solution is injected by intravenous bolus, and the remaining 90% is injected by intravenous drip

within 1h.

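### Alteplase is dosed at 0.9 mg/kg with no maximum, while the test drug is capped at 25 mg and the cited phase 3 trial capped the same alteplase regimen at 90 mg

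*Supplement*

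**What the plan says.** The control-arm instruction in protocol section 5.3 reads "The amount required for medication is calculated and measured according to the actual body weight of the subject. 10% of the solution is injected" by bolus, with the remaining 90% dripped in within an hour. The protocol summary has the same text ("to the actual body weight of the subject. 10% of the solution is injected by intravenous bolus, and the" remainder by drip). Section 1.4 has the dose "measured according to the actual body weight of the subject based on a standard of 0.9 mg rt-PA/kg". SAP section 5 has it "according to the actual body weight of the patient based on a standard of 0.9 mg rt-PA/kg", and SAP section 9 defines the control group as "rt-PA 0.9mg/kg: The product is dissolved in sterile water for injection" and then by actual weight. None of the five gives a maximum.

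The test-arm text is different. The section 5.3 heading is "Treatment group (rhTNK-TPA 0.25mg/kg, 25mg at most", and the same limit appears in the summary, section 1.4, Appendix 1, and SAP sections 5 and 9. In section 1.4 and in both SAP sections, the capped and uncapped regimens stand next to each other.

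The one alteplase maximum in the current text is in protocol section 1.3. It describes the control arm of the cited phase 3 tenecteplase trial as "alteplase at 0.9 mg/kg (maximum 90 mg".

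**The concern.** This is a dosing instruction for a thrombolytic. Section 9.5 of the protocol puts bleeding first among the expected adverse reactions, and section 9.7 quotes symptomatic intracranial hemorrhage at 2% to 7%. The stated rule takes any control patient above 100 kg past the only alteplase ceiling the documents mention. A test patient of the same weight is held at 25 mg. No reason is given for treating the arms differently.

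Nor can a site's own judgement be relied on to close the gap cleanly. Section 15 says: "All requirements specified in the study protocol must be strictly implemented". A site that limits alteplase to 90 mg on its own initiative departs from the written dose. A site that complies exceeds 90 mg. Poor compliance with stipulated medication is also a possible ground for per-protocol exclusion (protocol 12.1, SAP 7), so heavy controls could be classified inconsistently.

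**Working it through.** **1. Does any other text supply a maximum for the control arm?**
- Eligibility (protocol 4.1 and 4.2): no upper weight limit.
- Drug labels (5.2): the instruction to consult the package insert is on the test-drug outer box. The control-drug label does not carry it, and its note only asks for the vial strength to be chosen by the actual dose.
- Appendix 1: covers the test drug only.
- Concomitant treatment (6.2): names a general 2018 stroke guideline for enrolment and later management, and two endovascular guidelines in the sentence on thrombolysis. It states no alteplase maximum.

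Nothing in the current protocol or SAP fills the gap.

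**2. At what weight does each cap apply?** Weight = cap ÷ dose per kg.
- Test drug: 25 ÷ 0.25 = 100 kg.
- Alteplase in the cited trial: 90 ÷ 0.9 = 100 kg.

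The two caps therefore match exactly. A 90 mg limit would make both arms level off at the same weight.

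**3. Dose as written above 100 kg** (alteplase = 0.9 × weight; test drug = 25 mg)

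| Weight | Alteplase as written | Excess over 90 mg | Test drug |
|---|---|---|---|
| 105 kg | 94.5 mg | 5% | 25 mg |
| 110 kg | 99 mg | 10% | 25 mg |
| 120 kg | 108 mg | 20% | 25 mg |

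**4. How many controls?** The documents give no weight distribution, so these are assumptions: normal weights, 715 controls as planned.

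| Assumed mean / SD | Share above 100 kg | Controls above 100 kg | Their mean weight | Their mean dose (× 0.9) | Controls above 110 kg |
|---|---|---|---|---|---|
| 65 / 11 kg | 0.073% | 0.52 | 103.0 kg | 92.7 mg | 0.02 |
| 68 / 12 kg | 0.383% | 2.74 | 103.7 kg | 93.3 mg | 0.17 |
| 72 / 14 kg | 2.275% | 16.27 | 105.2 kg | 94.7 mg | 2.37 |

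**5. Trial-level effect, on a deliberately pessimistic assumption.** Suppose the excess doubles the risk of symptomatic hemorrhage in every control above 100 kg, with baseline risk at the protocol's 2% to 7%.
- Extra events: from 0.52 × 0.02 = 0.01 to 16.27 × 0.07 = 1.14.
- Expected events among controls without the excess: 715 × 0.02 = 14.3 to 715 × 0.07 = 50.1.

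Now let each extra event also cost one good outcome (mRS 0-1) in the control arm.
- Planning risk ratio from the stated rates: 0.6364 ÷ 0.5932 = 1.0728.
- Control rate lost at most: 1.14 ÷ 715 = 0.0016, giving 0.5932 − 0.0016 = 0.5916.
- Risk ratio then: 0.6364 ÷ 0.5916 = 1.0757.

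The shift favours the test drug but is about 0.003.

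**The case against.** The best counter-argument is that this is drafting shorthand, and that no uncapped regimen was intended. The comparator is repeatedly called standard, it is a marketed product, and section 6.2 places patients under a national stroke guideline. Section 6.3 requires an administration table and the dosage to be checked before dosing; that table is not in the supplement. Any of these might carry a maximum. Several other alteplase regimens in the background, including the sponsor's phase 2 trial, are also given at 0.9 mg/kg without one. It can be added that the 90 mg figure describes another trial's regimen, that no document gives a dose-bleeding relation above 90 mg, that few patients weigh so much, and that the SAP texts describe the regimen and do not instruct sites.

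Much of this stands. Sites may well cap in practice, so an actual overdose is possible but not shown, and the doubling of hemorrhage risk used above is an assumption. The numbers affected are small and the typical excess is 3% to 5%. None of it supplies the missing limit, however. No current text states a control-arm maximum, and a protocol that demands strict implementation should not depend on sites correcting its dose from elsewhere.

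**Conclusion.** The concern holds. All five current alteplase regimens lack a maximum, the test-drug regimen has one throughout, and followed as written the control dose passes 90 mg for anyone over 100 kg. The excess is 0.9 mg for each further kilogram.

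This is a matter of individual safety and of an unambiguous instruction. It does not threaten the trial's conclusion: even under the heaviest assumed weight distribution and a doubled hemorrhage risk, about one extra event is expected and the planning risk ratio barely moves. The patient counts rest on assumed weight distributions and the bleeding figures on an assumed risk increase. The dose arithmetic rests on the documents alone. The correction should be made, with confidence in its practical importance only moderate.

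**What to change.** State a 90 mg maximum for alteplase in the control-arm text of the protocol summary, protocol sections 1.4 and 5.3, and SAP sections 5 and 9, in the same form as the test-drug limit. Section 5.3 is the operative dosing text; the other four should agree with it. Send sites a short note drawing attention to the limit.

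The cost is one phrase in five places and the note. Sample size, non-inferiority margin and analysis are unaffected.

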#### 5.4 Drug storage conditions

Study drugs will arrive at the research centers prior to the launch of the center, and then sufficient study drugs will be supplied to the Center on a regular basis based on the actual number of enrolled subjects and the amount of drugs to be used. The study drug will be stored in a secure location under the direct responsibility of the investigator or other authorized person and will be stored in accordance with the conditions described on the label.

#### 5.5 Drug distribution and inventory

The investigator must keep accurate records of the number of boxes/bags of the drug being studied. In this study, the drug is administered intravenously, and the study drug had to be administered by the investigator.

#### 5.6 Drug recovery and destruction

Investigators are required to record information on all study drug dispensations, including date, quantity, drug lot number, and subject number. Used and unused drugs must be recovered and destroyed in accordance with relevant regulations and procedures.

